Domain 4 (exploratory outcomes: HIV/PrEP linkage outcomes): (a) number of HIV+ youth referred to HIV treatment at 3, 6, and 12 months FUs, (b) number of HIV+ youth attending at least one treatment appointment at 3, 6, and 12 months FUs; (c) number of youth behaviorally PrEP eligible referred to PrEP/medical care at 3, 6, and 12 months FUs, (b) number of youth behaviorally PrEP eligible attending at least one HIV care appointment care at 3, 6, and 12 months FUs.

TRIAL MANAGEMENT

Study/data collection sites

Data will be collected at **Brooklyn Justice Initiative (BJI), run by Center for Court Innovation**. BJI is an alternative sentencing program (ASP) for JIY processed through Brooklyn Criminal Court. BJI aims to reduce re-offending and increase public safety; promote use of meaningful social services; provide rigorous compliance monitoring; and reduce criminal convictions and use of jail. Located in the Brooklyn Criminal Courthouse, BJI serves 9,000 youth/year; almost all (94%) are mandated to BJI for ≤ 15 days.

Study sample description

To address the study aims we will collect data from a sample of youth aged 18-24 who have been placed in BJI (sample 1), from a sample of HIV testing outreach staff (sample 2) and from staff at BJI (Sample 3).

Sample size and power

The total sample size of sample 1 will comprise N=472 youth currently enrolled at BJI: n=14 youth will serve on an advisory panel to provide feedback as MOVE and NYSBIRT are adapted; n=8 youth will pilot test the adapted Link2CARE protocols prior to the efficacy test of Link2CARE; and n=450 youth will be randomly assigned (1:1) to either Link2CARE or standard of care. Sample 2 will comprise N=2 Project STAY outreach workers who will be embedded at BJI and will deliver all elements of Link2CARE to youth. Sample 3 sample size is expected to be all 15 staff who work at BJI.

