Based on our previous work, the retention rate for studies of JYI was about 75% to 80%. Even though we anticipate being able to maintain 20% attrition, we conservatively use 25% attrition at 12-month FU in this power calculation. Under such assumptions and with a baseline sample of 450 participants, we estimate a final sample of at least n=338 with complete data for the primary analysis at 12-month FU. With 169 participants per group and the use of Bonferroni correction, we will be able to provide 80% power to detect a standardized effect size of .35 or more on any of the three primary outcomes (i.e., total number of unprotected anal and vaginal sex occasions in past three months, acceptance of HIV testing at initial offering; and frequency of substance use in past 30 days). The standardized effect size of .35 is considered as a relatively small to moderate effect size according to Cohen⁴ and our previous study suggests that it is an achievable effect. A substantial increase in sample size will not strongly impact effect size – e.g. to reduce the standardized effect size from .35 to .32, 100 more participants (22% increase in current sample size) would be required. Even if actual attrition is greater than expected e.g. say 30%, the detectable standardized effect size will only increase slightly to .36. Furthermore, as we will impute missing data using informative covariates for the primary analyses and using a less conservative Holm procedure for multiple comparison adjustment, power to detect such effects will actually be greater than 80%.

Table 1. Inclusion/exclusion criteria

Study Phase	Study Sample	Inclusion Criteria	Exclusion Criteria
Phase 1: Adaptation for Link2CARE	Peer advisory panel n=14	1) Between 18-24 years of age 2) Currently enrolled in BJI 3) Conversant in English (in the past two years, only two JIY at BJI have required language assistance).	1) Medical or psychiatric illness requiring hospitalization 2) Serious suicidal or homicidal ideation
	BJI staff n=6	1) Currently employed at BJI	None
Phase 2: Link2CARE Efficacy Trial and Implementation Evaluation	Pilot Youth n=8	1) Between 18-24 years of age 2) Currently enrolled in BJI 3) Conversant in English (in the past two years, only two JIY at BJI have required language assistance).	1) Medical or psychiatric illness requiring hospitalization 2) Serious suicidal or homicidal ideation

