Analysis plan for Specific Aim 1. Prior to conducting our multivariable analyses, we will examine study variables using descriptive statistics, testing for differences across demographic characteristics (e.g., race/ethnicity, age) using t-tests, ANOVAs, and Chi-squares, as appropriate. Systematic baseline differences are not expected; however, any parameters that differ across conditions at baseline will be included as covariates in subsequent models. We will calculate descriptive summary statistics corresponding to study variables at each follow-up (FU) to understand any temporal patterns, as well as compare the two groups in terms of average change from baseline to 12-months post-baseline. We will use the general framework of generalized linear models (GLM) to model the longitudinal outcome trajectories and GEE method to account for within-subject correlation across the four time points (baseline, 3-, 6-, and 12-months). Stratified randomization of participants to the groups based on their gender requires that the analysis also include gender as covariate. The general form of the analysis model will be $g(\mu) = \alpha_0 + \alpha_1 X + \beta I + \sum \gamma_i T_i + \sum \delta_i T_i I$, where g denotes the link function (identity for continuous outcome, logit for binary outcome and natural log for count outcomes) X represents the indicator of female (vs. male), I is the group indicator for Link2CARE (vs. SOC), and T_i is the indicator for time at 3-month, 6-month, and 12-month evaluation (vs. baseline) for $i=1, 2, \text{ and } 3$. The interaction coefficients δ_i are of interest, measuring the difference in the rate of change in outcome across the two treatment groups at each follow-up assessment. We will employ the above analytic approach to examine differences between youth in Link2CARE and in the SOC condition with respect to key study parameters within these four domains detailed below. Proposed hypotheses are that the experimental arm (Link2CARE) would have better outcomes (e.g. greater reduction on total number of unprotected anal and vaginal sex occasions in past three months from baseline to 12 month FU; greater increase in proportion of acceptance of HIV testing at initial offering; greater reduction on frequency of substance use in past 30 days at 3-, 6- and 12-month FUs; and of those referred to SU treatment, a greater number of youth attending intake plus one treatment session at 3-, 6- and 12-month FUs)

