compared to the standard of care; all hypothesis tests will be conducted under the control of familywise error rate no greater than 0.05 level. The Holm step down procedure will be employed to adjust for multiple comparisons.

1. **Domain 1 (primary outcomes: HIV outcomes):** (a) total number of unprotected anal and vaginal sex occasions in past three months at 12 month FU; (b) acceptance of HIV testing at initial offering (y/n), (c) any HIV testing between 6-month and 12-month FU (y/n).
2. **Domain 2 (SU outcomes):** (a) frequency of youth substance use in past 30 days at 3-, 6- and 12-month FUs; (b) number of youth referred to SU treatment at 3-, 6- and 12-month FUs; at (c) number of youth attending intake plus one treatment session at 3-, 6- and 12-month FUs.
3. **Domain 3 (exploratory outcomes: HIV/PrEP linkage outcomes):** (a) number of HIV+ youth referred to HIV treatment at 3, 6, and 12 months FUs, (b) number of HIV+ youth attending at least one treatment appointment at 3, 6, and 12 months FUs; (c) number of youth behaviorally PrEP eligible referred to PrEP/medical care at 3, 6, and 12 months FUs, (b) number of youth behaviorally PrEP eligible attending at least one HIV care appointment care at 3, 6, and 12 months FUs.
4. **Domain 4 (STI testing outcomes):** a) acceptance of STI testing at initial offering (y/n), (b) any STI testing between 6-month and 12-month follow up; (c) number of STI+ youth referred to STI treatment at 3, 6, and 12 months FUs; (d) number of STI+ youth attending ≥ 1 treatment appointment at 3, 6, 12 months FUs.

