
Analysis of participant attrition and missing data. We will make every effort to retain participants in the study to avoid bias due to attrition. For those individuals who refuse continued participation, we will document reasons for study discontinuation and Rubin's multiple imputation method with 11 repeated imputations will be

employed to impute the missing endpoint for conducting the intent-to-treat analysis.

QUALITY ASSURANCE

Procedures in place to ensure the validity and integrity of the data

All data collection protocols include a form on which research staff members record any problems with the data collection or unusual occurrences during the collection. They also are encouraged to bring problems to the attention of the Project Director, or PI. These members of the research staff also meet on a regular basis to identify and address any issues that arise. These procedures allow our research staff an opportunity to quickly review and respond to any possible concerns. We expect missing data to be minimal, nevertheless regular (quarterly) quality assurance checks will be made by the Project Director to identify any systematic missing information and remedies will be enacted.

Procedures to guarantee the accuracy and completeness of the data, during data collection, entry, transmission, and analysis.

To check for errors in data entry, we will adhere to the following protocol. All face-to-face surveys will be recorded. One out of every seven recordings for each interviewer will be compared to the entered interview. If we identify a proportion of errors that is more than 1% error, we will temporarily suspend the interviewer from active interviewing. We will listen to all interviews for comparison purposes, identifying any errors and will re-train the interviewer to ensure accuracy and completeness of all face-to-face survey interviews. A subset (10%) of all data from hard-copy/paper-pencil instruments that is entered into the project database will be similarly checked. If we identify a proportion of errors that is more than 1% error, we will reenter all questionnaires and subsequently compare both data sets. We will go back to the original surveys to resolve all inconsistencies. To prevent data entry problems we will prepare a data entry system that will alert us when data are entered that are out of range.

Procedures for preventing and addressing breaches of confidentiality

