Only two of the three co-primary endpoints will be monitored for early stopping: (1) total number of unprotected anal and vaginal sex occasions in past three months at 12 month FU; (2) any HIV testing between 6-month and 12-month FU (y/n). We will follow a modified Haybittle-Peto rule⁷ to propose early stopping as follows: the z-score for testing the null hypothesis for each of the two primary outcomes will be calculated once during interim analyses (see below) when one-quarter of the expected total 12-month outcome data has been observed (after approximately 6-months of 12-month data collection). This will allow the PSMB to recommend continuing to recruit subjects or stop the trial for strong positive or negative efficacy prior to the end of subject recruitment.

The z-score for early stopping will be $Z = 3.6623$ for either monitored outcome, corresponding to a normal two-tailed critical value cutting off nominal probability 0.00025 in each tail. It follows that either endpoint may suggest early stopping with total two-tailed probability 0.0005 under the null hypothesis and therefore the probability of early stopping under the null hypothesis for either endpoint in either direction will be no greater than 0.001. This stopping rule is less conservative than an O'Brien-Fleming-like alpha spending function monitoring plan, yet is still sufficiently conservative to leave the terminal significance criteria nearly unaffected. In particular, assuming no early stopping, if either of the two monitored co-primary endpoints specified above possesses the smallest P -value among all three co-primary endpoints, the group comparison will be declared significant at the 0.05 level (adjusted for multiple comparisons) if the terminal z-score criterion is $Z = 2.3978$ or greater. This Z -score is very close to the nominal $0.05/3 \approx 0.01667$ two-tailed normal critical value of 2.3940, which is the initial required criterion under the Holm step-down procedure without sequential monitoring. If the unmonitored co-primary endpoint (acceptance of HIV testing at initial offering, y/n) should have its P -value as smallest and less than or equal to $0.05/3 \approx 0.01667$, then it will be declared significant (at the two-tailed 0.05 level, adjusted for multiple comparisons).

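### Covariates entered only as main effects do not correct the tested group-by-time contrast for chance imbalance in repeated outcomes such as unprotected-sex occasions

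*Combined protocol and SAP*

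**What the plan says.** The combined protocol and SAP, under Analysis plan for Specific Aim 1, states that randomization stratified by gender "requires that the analysis also include gender as covariate". Any variable that differs between conditions at baseline is also to be added as a covariate to later models.

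The general model written there contains an intercept, one gender term, one group term, three time indicators (3, 6 and 12 months against baseline) and three group-by-time terms. It is fitted by GEE, with a log link for counts. It has no gender-by-time term. The group-by-time coefficients are the ones of interest, described as "measuring the difference in the rate of change in outcome across the two treatment groups at each follow-up assessment". The section gives neither the variance function for counts nor the working correlation, and it does not write out how the added covariates enter.

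Under Analysis of participant attrition and missing data, multiple imputation is to be "employed to impute the missing endpoint for conducting the intent-to-treat analysis", for individuals who refuse continued participation.

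Aim 1 tests are held to "control of familywise error rate no greater than 0.05 level" by the Holm procedure. Under Trial Stopping Rules, the first Holm step without monitoring corresponds to a "two-tailed normal critical value of 2.3940". The number of unprotected-sex occasions is one of three co-primary outcomes and one of the two that are monitored.

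**The concern.** The plan presents covariate adjustment as something stratification requires and as its remedy for baseline imbalance. Yet the covariates sit in a part of the model that has little or no bearing on the tested coefficient. A main effect shifts an arm's mean at every visit by the same amount on the link scale. The tested contrast is a change from baseline compared between arms, so that shift is removed whether or not the covariate is in the model.

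What the contrast does not remove is a covariate's effect on the change itself. If such a covariate is unbalanced by chance, its effect on the 12-month change passes into the treatment estimate, and a main effect does not take it out. A co-primary result would then be reported as adjusted for imbalance when, for this purpose, it is not.

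**Working it through.** **Inputs from the document.** N=450 allocated 1:1, 25% attrition at 12 months and 169 evaluable per arm (Sample size and power); 28% female (Target population distribution); first-step alpha 0.05/3, two-sided (Trial Stopping Rules); model and links as described above.

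**Assumptions for the simulations, not in the document.** Overdispersed counts and a second covariate unbalanced by about 0.2 SD. For steps 3 and 5, a female log rate ratio of 0.5. For step 4, a log-rate slope of 0.25 for the second covariate on the 12-month change.

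**Step 1: the plan's own power figure.** "With 169 participants per group and the use of Bonferroni correction", the plan claims "80% power to detect a standardized effect size of .35 or more".
- n per arm = 2 × (2.3940 + 0.8416)² / 0.35² = 2 × 10.469 / 0.1225 = 170.9, so 171 against the stated 169. Power at 169 is 79.5%.
- Detectable effect = 3.2356 × √(2/n). This gives 0.352 at n = 168.75 (450 with 25% attrition), 0.319 at 206.25 (550 with 25%) and 0.365 at 157.5 (450 with 30%). The plan states .35, .32 and .36.

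The figures reproduce and take no credit for covariate adjustment.

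**Step 2: algebra.** Write the mean for arm g at visit t as exp(a·X) × m(g,t), with X constant over time. With Poisson variance, independence working correlation and complete data, the score equations for the arm-by-visit cells give

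m(g,t) = ȳ(g,t) / E(g), where E(g) is the mean of exp(a·X) in arm g.

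E(g) is the same at baseline and at 12 months, so m(g,12)/m(g,0) = ȳ(g,12)/ȳ(g,0). The 12-month coefficient is the log ratio of these two within-arm ratios and does not depend on a. An identity link with Gaussian variance behaves the same way, with differences in place of ratios.

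**Step 3: numerical check of the cancellation.** In one simulated trial (Poisson variance, complete data), models with no covariate, with gender, and with gender plus the second covariate all gave coefficient −0.39592, robust SE 0.12829 and z −3.0861. This held under both independence and exchangeable correlation. Over 60 trials the largest change in z was 0.000000.

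The cancellation is not exact in other settings. Absolute change in z against the model with no covariate (60 trials each, independence):

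| Setting | Gender: median (max) | Gender + second covariate: median (max) | Trials crossing 2.394 |
|---|---|---|---|
| Negative binomial, complete | 0.14 (0.72) | 0.25 (1.17) | 1 and 9 |
| Poisson, 25% of 12-month rows missing at random | 0.04 (0.24) | 0.11 (0.53) | 1 and 3 |
| Poisson, dropout depending on gender and arm | 0.27 (0.69) | 0.24 (0.61) | 5 and 4 |

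Under negative binomial variance the SE fell by about 2% with gender and 4% with both covariates. Other assumed settings gave reductions of 5 to 12%.

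**Step 4: does the movement correct the imbalance?** Null trials, 60 per setting, imbalance 0.22 SD and slope 0.25. The shift to be removed is about 0.22 × 0.25 = 0.055. Mean 12-month coefficient:

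| Setting | No covariate | Main effects | Covariate-by-time | Removed by time terms |
|---|---|---|---|---|
| Poisson, independence | 0.052 | 0.052 | 0.002 | 0.050 |
| Poisson, exchangeable | 0.073 | 0.073 | 0.019 | 0.054 |
| Neg. binomial, independence | 0.082 | 0.083 | 0.033 | 0.050 |
| Neg. binomial, exchangeable | 0.059 | 0.061 | 0.010 | 0.051 |
| Poisson, 25% of 12-month rows missing | 0.019 | 0.021 | −0.026 | 0.047 |

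The levels carry simulation noise; the last column is the difference between main effects and time terms. Main effects removed essentially none of the shift. The time terms moved z by a median of about 0.3.

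**Step 5: gender alone.** With Poisson variance, complete data and no true gender-by-time effect, adding gender-by-time gave an SE ratio of 0.999 and a median change in z of 0.001 (maximum 0.04).

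**The case against.** A reader might infer that the adjustment always leaves the unprotected-sex test untouched. The documents do not support that. The plan fixes the link but not the variance function, and negative binomial variance is a plausible choice for an overdispersed count. Under it, main effects move z and narrow the SE. Nor are complete data assured: imputation is described for the missing endpoint of those who refuse continued participation, which does not clearly cover youth who cannot be reached or who miss a 3- or 6-month visit. This stands, and it limits the exact cancellation to Poisson-type variance (or a Gaussian identity model) with complete data. It does not rescue the adjustment as a remedy for imbalance, as step 4 shows.

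It is also fair that the form of the added covariates is inferred from the one model shown, which is called a general form. If time interactions are intended, they are not stated.

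Cancellation is also how a change-from-baseline contrast works: constant covariate differences are already removed. Only a predictor of change matters, and the assumed imbalance is uncommon. With "n=450 youth will be randomly assigned (1:1) to either Link2CARE or standard of care", the SD of a chance imbalance is √(2/225) = 0.094. An imbalance of 0.20 to 0.25 SD is therefore a 2.1 to 2.7 SD event for any one covariate (two-sided p about .034 to .008). This keeps the consequence modest. But these are the covariates most likely to be picked up by the plan's rule of adjusting for baseline differences, so the remedy would fail in the cases it is meant for.

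Finally, interaction terms are one of several acceptable models. That is true; the point is that the written model does not deliver the stated correction.

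**Conclusion.** The point holds in a limited form. For outcomes with a baseline measurement, covariates entered as main effects do not correct the tested group-by-time coefficient for imbalance in a predictor of change. With log link, Poisson-type variance and complete data the adjusted and unadjusted tests are identical. Otherwise they can differ, with some gain in precision, but most or all of the imbalance remains. For an imbalance of about 0.2 SD and a slope of 0.25, that is about 0.04 to 0.06 on the log scale, or a factor of exp(0.04) = 1.04 to exp(0.06) = 1.06 in the ratio of rate ratios. This size rests on the assumed slope and imbalance; the exact cancellation does not.

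Three stronger readings are tempting but unsupported:
- **Bias or an inflated error rate.** Randomization protects the unconditional error rate; the issue is conditional on a chance imbalance.
- **A wrong sample size.** The power figures use no covariate and stand.
- **A flaw in all three co-primaries.** The two HIV-testing outcomes are each measured once, so their test is the group effect and main-effect covariates do bear on it.

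For gender alone the consequence is negligible, since stratification balances it. The reason to act is that the plan promises a correction its written model does not make, on a monitored co-primary outcome.

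**What to change.** In the model statement for Specific Aim 1:

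1. For outcomes with a baseline measurement, add gender-by-time terms and covariate-by-time terms for a short list of baseline covariates named before the data are seen.
2. For the two once-measured HIV-testing outcomes, keep gender and the named covariates as main effects.
3. State the variance function for the count outcomes.

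The cost is a line or two of text and three extra parameters per covariate (3, 6 and 12 months), which is why the list should be short. Trial conduct, sample size and the multiplicity procedure do not change.

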HIV and STI testing: Following randomization and baseline assessment, all youth will be offered an HIV and an STI test for Chlamydia and gonorrhea; initial testing will take place onsite at BJI. All youth will also be offered HIV and STI testing at each follow-up interview (3m, 6m and 12m). **HIV testing** will be done using Oraquick advance rapid HIV test. Following brief pre-test counseling, an oral swab will be used to collect saliva to conduct HIV rapid test. Once conducted, the embedded Project STAY staff member (LINK2CARE condition) or human subjects-trained RA (standard of care) will provide results to the participant and HIV+ JIY will be immediately linked to care following Link2CARE linkage protocols. The Project STAY staff or RA will then place the swab in a closed Developer Solution vial, then back into the package. The entire package will be placed in a baggie. The baggie with the used test will be brought back to NYSPI by human-subjects trained RAs and turned in to the Project Director who will enter the results into a the project database at NYSPI that is held on a secure server. The baggie containing the used OraQuick test and materials will then be disposed of in the appropriate waste container. Staff (interviewers and office staff) will wear gloves when manipulating test materials. **STI testing** will occur by the collection and processing of the urine specimens using a Gen-probe APTIMA Urine Specimen Collection Kit for Male and Female Urine Specimens. The testing kits are provided and the urinalysis will be performed by the New York City Department of Health (NYCDOH) at no cost as part of an ongoing agreement with Project STAY. The client is instructed about how to provide the urine sample, and is sent to the bathroom by either the embedded Project STAY staff member (LINK2CARE condition) or human subjects-trained RA (standard of care). Upon return, the Project STAY staff member or RA packages the sample and arranges for pickup by the Department of Health's (DOH) Bureau of STD control. NYCDOH uses the third generation nucleic acid amplification test (NAAT), yielding qualitative testing results. Specimens will be collected and transferred into their respective specimen transport tubes. The transport solutions in these tubes release the rRNA targets and protect them from degradation during storage. When the APTIMA Combo 2 Assay is performed in the laboratory, the target rRNA molecules are isolated from specimens by the use of capture oligomers in a method called target capture. After the target capture steps are completed, the specimens are ready for amplification. The GEN-PROBE APTIMA Combo 2 Assay replicates a specific region of the 23S rRNA from CT and a specific region of the 16S rRNA from GC via DNA intermediates. A unique set of primers is used for each target molecule. Differences in the kinetic profiles of the CT and GC labeled probes allow for the differentiation of signal; kinetic profiles are derived from measurements of photon output during the detection read time. The chemiluminescent detection reaction for CT signal has very rapid kinetics and has the "flasher" kinetic type, while the detection reaction for GC signal is relatively slower and has the "glower" kinetic type. Assay results are determined by a cut-off based on the total RLU and the kinetic curve type. Written documentation of the test results will be obtained by the research office from the NYCDOH Microbiology laboratory within 7 days after the urine sample was delivered. The Project Director who will enter the results into a the project database at NYSPI that is held on a secure server Respondents randomized to Link2CARE who test positive will be informed by embedded Project STAY staff of their results and will immediately be linked to care by STAY staff following Link2CARE linkage protocols. Respondents randomized to SOC who test positive will be contacted by study staff using a succession of methods (telephone, registered letter, and, if refused or undelivered, regular mail). Participants will be informed that antibiotics are used to treat Chlamydia and Gonorrhea. We will counsel that all sex partners within the last 60 days should be evaluated and treated and to avoid sex until they and their partners have been treated for at least 7 days or 7 days after a single dose treatment. Specific referral procedures will be followed to maximize chances that participants will seek treatment.

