Intent-to-treat principles will be invoked in the primary analysis. The primary aim is to determine whether participants randomized to Link2CARE show greater improvement in HIV outcomes from baseline to 12-month follow up than participants in SOC. Measurement of primary HIV outcomes includes three variables: number of unprotected sex occasions, whether participants accept HIV testing at initial offering (y/n), and any (repeat) HIV testing between 6-month and 12-month follow up (y/n). Other behavioral and linkage variables to be examined as secondary and exploratory outcomes are described in Section 3.3.9.3. Implementation outcomes to be examined include feasibility, acceptability, and sustainability. In addition, we will examine potential CFIR correlates of implementation, such as organization culture and climate and staff attitudes. Finally, mediators associated with service use as specified by the Andersen model will be examined, including motivation for treatment, perceived barriers to treatment, prior service utilization.

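### The time-by-arm coefficients named as the effects of interest cannot be estimated for two of the three co-primary outcomes, each a single yes/no value with no defined baseline

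*Combined protocol and SAP*

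**What the plan says.** The section Analysis plan for Specific Aim 1 sets out a generalized linear model fitted by GEE over four time points (baseline, 3, 6 and 12 months). It has an intercept, female gender X, arm I, three time indicators T1 to T3 with baseline as reference, and three time-by-arm products with coefficients δ1 to δ3. The plan names the δ coefficients as the target, "measuring the difference in the rate of change in outcome across the two treatment groups at each follow-up assessment". It then extends the approach to every domain: "We will employ the above analytic approach to examine differences between youth in Link2CARE and in the SOC condition". No other model for the Aim 1 comparisons is given.

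Two of the three primary outcomes in Domain 1 are "b) acceptance of HIV testing at initial offering (y/n), (c) any HIV testing between 6-month and 12-month FU (y/n". The STI domain has the same pair: "acceptance of STI testing at initial offering (y/n), (b) any STI testing between 6-month and 12-month follow up". The HIV and STI testing paragraph places the first offer after allocation: "Following randomization and baseline assessment, all youth will be offered an HIV and an STI test for Chlamydia and gonorrhea".

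The hypotheses are nonetheless worded as change. The Data analysis plan frames the primary aim as "greater improvement in HIV outcomes from baseline to 12-month follow up than participants in SOC", and the hypothesis for (b) is a "greater increase in proportion of acceptance of HIV testing at initial offering".

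Trial Stopping Rules then uses P-values for all three co-primaries in a Holm procedure, and interim z-scores for unprotected sex occasions and for (c). It does not say which coefficient supplies them.

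**The concern.** A time-by-arm coefficient is a difference between two arm contrasts, one at a follow-up visit and one at the reference time. It needs the outcome on at least two occasions, one of them the reference. Outcome (b) occurs once, after randomization, so it has no pre-randomization value. Outcome (c) summarizes one interval, and the documents define no baseline version of it.

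An analyst who follows the plan literally would therefore get no estimate of the named coefficient for (b) or (c) and would have to choose another test. Those tests feed two of the three Holm P-values and the interim stopping statistic for (c). The critical values for those decisions are fixed to four decimal places, but the statistic to be compared with them is left open and could be settled after data have been seen.

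**Working it through.** **Inputs.** The model, the four time points and the logit link for binary outcomes come from Analysis plan for Specific Aim 1. N = 450 randomized 1:1, 25% attrition, n = 338 with complete 12-month data and 169 per arm come from Sample size and power. The 28% female share comes from Target population distribution. The one-quarter interim fraction comes from Trial Stopping Rules.

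**1. The plan's own power figure.** For a two-arm comparison at one time point, with standardized effect 0.35 and two-sided alpha 0.05/3 = 0.01667 (critical z = 2.3940):

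power ≈ Φ(0.35 × √(169/2) − 2.3940) = Φ(3.217 − 2.394) = Φ(0.823) ≈ 0.795.

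This reproduces the stated 80%. The power statement thus matches a simple arm comparison at one time point, and the present point does not affect it.

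**2. What each coefficient means.** The model is

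g(μ) = α0 + α1·X + β·I + Σ γi·Ti + Σ δi·Ti·I.

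The arm contrast is β at baseline and β + δi at visit i. Hence δi = (contrast at visit i) − (contrast at baseline).

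**3. Outcome (b), one record at the first offer (all Ti = 0).** The model reduces to

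logit(p) = α0 + α1·X + β·I.

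The three time columns and the three interaction columns are all zero. The rank is 3 of 9 at n = 450. β is estimable; none of δ1, δ2, δ3 is.

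**4. Outcome (c), one record at 12 months (T3 = 1).** The model reduces to

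logit(p) = (α0 + γ3) + α1·X + (β + δ3)·I.

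The T3 column equals the intercept and the T3·I column equals I. The rank is again 3 of 9. Only the sum β + δ3 is estimable; β alone and each δi alone are not. The result is the same at n = 338 (complete data), n = 450 (every missing endpoint imputed) and n = 84 (interim, 0.25 × 338 = 84.5).

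**5. Contrast with a repeated outcome.** For unprotected sex occasions, with all four time points, the rank is 9 of 9 and all three δi are estimable. The model suits that co-primary.

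**6. Do other rules in the plan rescue it?** The covariate rule, "any parameters that differ across conditions at baseline will be included as covariates in subsequent models", adds columns but no occasions. With three added covariates (an assumed number) the rank is 6 of 12 and still no δi is estimable. Multiple imputation fills in a missing value of the same single endpoint and also adds no occasion.

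**7. Is anything lost by testing the arm effect?** In 600 simulated data sets (200 each at n = 338, 450 and 84; assumed control rates of 30%, 50% or 70%; assumed arm log odds ratio 0.5), the z-score of β + δ3 from the nine-coefficient fit was compared with the arm z-score from a gender-adjusted logistic fit with one record per person. The largest absolute difference was below 1e-14. The algebra in step 4 implies this: they are the same test.

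| Outcome | Records per person | Rank | δi estimable | Arm effect available |
|---|---|---|---|---|
| (a) unprotected sex | 4 | 9 of 9 | 3 of 3 | β and each β + δi |
| (b) first-offer acceptance | 1 | 3 of 9 | 0 of 3 | β |
| (c) any test, months 6–12 | 1 | 3 of 9 | 0 of 3 | β + δ3 |

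**The case against.** The strongest defence is that the equation is offered as a general form. With one occasion the time terms drop out, leaving a gender-adjusted logistic model with an arm term, which is the valid test. The text also speaks of differences between arms, of comparison with standard of care and, in the stopping rules, of a group comparison. On this reading one clarifying sentence is missing and no result would change. That is right about the consequence: the arm comparison is available and loses nothing. It does not remove the gap. The reduced model drops every coefficient that the plan calls of interest and tests one that it does not name, and the general phrases about comparing groups do not withdraw the stated target.

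A second defence uses the repeat test offers at 3, 6 and 12 months. Stacking them with the first offer restores rank 9, but for a different outcome. The post-randomization first offer becomes the reference, so the effect on first-offer acceptance, which is endpoint (b) itself, falls in β. A benefit that stayed constant on the logit scale would give δi = 0.

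Third, the plan mentions earlier service use and HIV-testing history, so some prior testing information may be collected. It appears only among proposed mediators and as a possible modifier; it is not defined as a baseline for (c), and it cannot help (b). The change wording for (b) does sit in a list of examples, and correcting it is editorial.

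One further observation stands and widens the point. The referral and attendance outcomes are listed at 3, 6 and 12 months with no baseline. If each is analysed as a per-person value at those visits, T1 + T2 + T3 equals the intercept and the three products sum to I. The rank is then 9 − 2 = 7, and again no single δi is estimable.

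**Conclusion.** The concern holds. For co-primaries (b) and (c) and their two STI counterparts, none of the three coefficients named as the effects of interest can be estimated. This affects two of three co-primaries, one of two interim z-scores and two secondary outcomes. The result is algebraic and does not depend on event rates. It rests on reading each outcome as defined, one yes/no value per person, and on the absence of any baseline version in the documents.

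The defect lies in the specification of the target. The endpoints remain testable, the power figure is untouched, and no bias is claimed. It should be fixed because confirmatory and stopping decisions need a named statistic before data are seen.

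**What to change.** In Analysis plan for Specific Aim 1, state that (b), (c) and the two STI counterparts are each tested by the arm coefficient of a logistic regression with one record per person, adjusted for gender, with the plan's existing covariate and multiple-imputation rules applied as for the other outcomes. In Trial Stopping Rules, state that this test supplies the Holm P-values for (b) and (c) and the interim z-score for (c).

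Keep the δ contrast for outcomes with repeated measures and a baseline value, such as unprotected sex occasions. Reword the hypothesis for (b) as a higher proportion accepting under Link2CARE than under standard of care. In the same edit, name a target for the referral and attendance outcomes that have no baseline; the arm contrast at each visit, β + δi, is estimable for per-person values.

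The cost is SAP wording only. No new data or participants are needed.
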